9.4.2. Outcomes of interest

The outcomes of interest are listed in Table 3 below. These outcomes were based on the Investigator's Brochure (version 4.0 June 2021) and expert clinical judgment. The first occurrence of each outcome is defined based on the presence of at least one ICD-9-CM or ICD-10-CM diagnosis code identified in the inpatient or outpatient setting during the follow-up period.

Outcome of interest	Operationalization: ICD-10-CM code	Operationalization: ICD-9-CM code
Agranulocytosis	D70.2 Other drug-induced agranulocytosis D70.1 Agranulocytosis secondary to cancer chemotherapy	288.03 Drug induced neutropenia
Thrombocytopenia	D69.3 Immune thrombocytopenic purpura D69.59 Other secondary thrombocytopenia D69.6 Thrombocytopenia, unspecified D69.41 Evans syndrome D69.49 Other primary thrombocytopenia	287.31 Immune thrombocytopenic purpura 287.49 Other secondary thrombocytopenia 287.5 Thrombocytopenia, unspecified 287.30 Primary thrombocytopenia, unspecified 287.32 Evans syndrome 287.39 Other primary thrombocytopenia
Leukopenia	D72.810 Lymphocytopenia D72.818 Other decreased white blood cell count D72.819 Decreased white blood cell count, unspecified D70.8 Other neutropenia D70.9 Neutropenia, unspecified D70.0 Congenital agranulocytosis	288.51 Lymphocytopenia 288.59 Other decreased white blood cell count 288.50 Leukocytopenia, unspecified 288.09 Other neutropenia 288.00 Neutropenia, unspecified
Pancytopenia	D61.811 Other drug-induced pancytopenia	284.12 Other drug-induced pancytopenia
	D61.818 Other pancytopenia	284.19 Other pancytopenia

Hypersensitivity (including anaphylactic reactions and anaphylactic shock)	K52.2x Allergic and dietetic gastroenteritis and colitis M31.0 Hypersensitivity angiitis T78.2x Anaphylactic shock, unspecified T78.4x Other and unspecified allergy M36.4x Arthropathy in hypersensitivity reactions classified elsewhere	558.3 Allergic gastroenteritis and colitis 446.20 Hypersensitivity angiitis, unspecified 446.21 Goodpasture's syndrome 446.29 Other specified hypersensitivity angiitis 995.0 Other anaphylactic reaction, Not elsewhere classified (NEC) 995.3 Allergy, unspecified, NEC 713.6 Arthropathy associated with hypersensitivity reaction
Hyperlipidemia	E78.49 Other hyperlipidemia E78.5 Hyperlipidemia, unspecified	272.4 Other and unspecified hyperlipidemia
Hypertriglyceride mia	E78.1 Pure hyperglyceridemia	272.1 Pure hyperglyceridemia

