Hyponatremia	E87.1 Hypo-osmolality and hyponatremia	276.1 Hypo-osmolality and/or hyponatremia
hypomagnesemia	E83.42 Hypomagnesemia	275.2 Disorders of magnesium metabolism
Hypocalcaemia	E83.51 Hypocalcemia	275.41 Hypocalcemia
Hypokalemia	E87.6 Hypokalemia	276.8 Hypopotassemia
Diarrhea	R19.7 Diarrhea, unspecified	787.91 Diarrhea
Vomiting	R11.10 unspecified R11.11 without nausea	536.2 Persistent vomiting 078.82 Epidemic vomiting syndrome

version 2.0, 10 Fe	toruary 2022	
	R11.12 Projectile vomiting R11.13 Vomiting of fecal matter R11.2 Nausea with vomiting, unspecified	787.03 Vomiting alone 569.87 Vomiting of fecal matter 787.01 Nausea with vomiting
Abdominal distension	R14.0 Abdominal distension (gaseous)	787.3 Flatulence, eructation, and gas pain
Hepatobiliary injury	K71x Toxic liver disease K72x Hepatic failure, not elsewhere classified K72.00 Acute and subacute hepatic failure without coma K72.01 Acute and subacute hepatic failure with coma K72.10 Chronic hepatic failure without coma K72.11 Chronic hepatic failure with coma K72.90 Hepatic failure, unspecified without coma K72.91 Hepatic failure, unspecified with coma K73x Chronic hepatitis K73.0 Chronic persistent hepatitis, not elsewhere classified K73.1 Chronic lobular hepatitis, not elsewhere classified K73.2 Chronic active hepatitis, not elsewhere classified K73.8 Other chronic hepatitis, not elsewhere classified K73.9 Chronic hepatitis, unspecified K73.9 Chronic hepatitis, unspecified K74 Fibrosis and cirrhosis of the liver	573.3 Hepatitis, unspecified 570 Acute and subacute necrosis of liver 572.2 Hepatic encephalopathy. 572.8 Other sequelae of chronic liver disease 571.41 Chronic persistent hepatitis 571.49 Other chronic hepatitis 571.5 Cirrhosis of liver without mention of alcohol 571.9 Unspecified chronic liver disease without mention of alcohol 571.6 Biliary cirrhosis 571.42 Autoimmune hepatitis 571.8 Other chronic nonalcoholic liver disease 573 Other disorders of the liver 573.0 Chronic passive congestion of liver 573.8 Other specified disorders of liver 573.4 Hepatic infarction 572.3 Portal hypertension 572.4 Hepatorenal syndrome 573.5 Hepatopulmonary syndrome 573.9 Unspecified disorder of liver 782.4 Jaundice, unspecified, not of newborn

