K74.00 Hepatic fibrosis, unspecified K74.01 Hepatic fibrosis, early fibrosis K74.02 Hepatic fibrosis, advanced fibrosis K74.1 Hepatic sclerosis K74.3 Primary biliary cirrhosis K74.4 Secondary biliary cirrhosis K74.5 Biliary cirrhosis, unspecified K74.60 Unspecified cirrhosis of liver K74.69 Other cirrhosis of liver K75x Other inflammatory liver diseases K75.2 Nonspecific reactive hepatitis K75.3 Granulomatous hepatitis, not elsewhere classified K75.4 Autoimmune hepatitis K75.81 Nonalcoholic steatohepatitis (NASH) K75.89 Other specified inflammatory liver diseases K75.9 Inflammatory liver disease, unspecified K76x Other diseases of the liver K76.0 Fatty (change of) liver, not elsewhere classified K76.1 Chronic passive congestion of liver K76.2 Central hemorrhagic necrosis of liver K76.3 Infarction of liver K76.4 Peliosis hepatis K76.5 Hepatic venoocclusive disease

	10 1 cordary 2022	
	K76.6 Portal hypertension K76.7 Hepatorenal syndrome K76.81 Hepatopulmonary syndrome K76.89 Other specified diseases of liver K76.9 Liver disease, unspecified K77 Liver disorders in diseases classified elsewhere K71.6 Toxic liver disease with hepatitis, not elsewhere classified K71.2 Toxic liver disease with acute hepatitis K71.3 Toxic liver disease with chronic persistent hepatitis K71.4 Toxic liver disease with chronic lobular hepatitis K71.50 Toxic liver disease with chronic active hepatitis without ascites K71.51 Toxic liver disease with chronic active hepatitis with ascites R17 Unspecified jaundice	
Urticaria	L50.0 Allergic urticaria L50.1 Idiopathic urticaria L50.8 Other urticaria L50.9 Urticaria, unspecified	708.0 Allergic urticaria 708.1 Idiopathic urticaria 708.8 Other specified urticaria 708.9 Urticaria, unspecified
Angioedema	T78.3XXA Angioneurotic edema initial encounter T78.3XXD Angioneurotic edema subsequent encounter T78.3XXS Angioneurotic edema sequela	995.1 Angioneurotic edema, not elsewhere classified

10 February 2022

2.0,

Version

version 2.0, 101	editiary 2022	Ī
Stevens- Johnson syndrome	L51.1 Stevens-Johnson syndrome L51.3 Stevens-Johnson syndrome -toxic epidermal necrolysis overlap syndrome	695.13 Stevens-Johnson syndrome 695.14 Stevens-Johnson syndrome- toxic epidermal necrolysis overlap syndrome
Lyell syndrome	L51.2 Toxic epidermal necrolysis [Lyell]	695.15 Toxic epidermal necrolysis

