9.10. Strengths and limitations of the research methods

This study has several strengths. It is a population-based study, and while the use of IV pantoprazole in infants aged 1 month to <1 year and patients aged 1 to <2 years is rare, this database includes a relatively large number of IV pantoprazole users in these age groups, facilitating generation of precise incidence rates. Given the age of the study population, it is less likely that patients will seek health care outside of the Optum EHR system during the baseline period, and therefore, it is less likely that an outcome of interest occurring during the baseline period will be missed; thus prevalent conditions are unlikely to be mistaken for incident events. Similarly, given the relatively short follow up time, it is less likely that patients will seek care outside of the Optum EHR system during this period, and therefore, that incidence events will be missed.

The study also has several limitations. As is the case in any administrative claims-based study without outcome validation/adjudication, outcome misclassification is a possibility. Diagnosis codes may be incorrect, or may be included as part of the diagnostic rule-out process rather than an indication of diagnosis itself. Conditions not requiring treatment or office visits tend to be systematically undercoded in such databases. It is possible that this study will only capture severe manifestations of such disorders. However, this limitation is likely to be applicable to two outcomes of interest -vomiting and diarrhea as patients experiencing these symptoms may not always visit a physician for care. Another well-recognized limitation of claims database analysis is that the gap between disease onset and date of diagnosis. However, in an incidence analysis, the time at risk begins on the date of IV pantoprazole administration (ie index date), not at disease onset. For outcome events, as only the incidence of new events is considered that occur after the initiation of IV pantoprazole, the impact of this limitation is expected to be minimal, as complications arising in infants would almost certainly be captured in the inpatient setting. Additionally, this would result in underestimating the incidence rate as time at risk would be inflated.

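### Table 3 counts some congenital, chronic, cirrhosis, sequela and late-effect codes as incident events, so long-standing disease first coded in follow-up raises those rates by an unknown amount

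*Protocol*

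**What the plan says.** Section 9.4.2 sets the event rule: "The first occurrence of each outcome is defined based on the presence of at least one ICD-9-CM or ICD-10-CM diagnosis code", from an inpatient or outpatient record during follow-up. There is no requirement on acuity, confirmation or onset. Under section 9.8, follow-up starts on the index date and ends no later than 90 days after IV pantoprazole is discontinued. Sections 9.3.1 and 9.8 remove from each outcome's analysis any child with a history of that outcome before the index date.

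Table 3 then lists, among others:
- Leukopenia: "D70.0 Congenital agranulocytosis".
- Angioedema: "T78.3XXS Angioneurotic edema sequela".
- Injection site thrombophlebitis: ICD-9-CM 909.3, a late-effect code.
- Hepatobiliary injury, ICD-9-CM: "571.41 Chronic persistent hepatitis 571.49 Other chronic hepatitis 571.5 Cirrhosis of liver without mention of alcohol", and also 571.6, 571.8, 571.9 and 572.8 (sequelae of chronic liver disease).
- Hepatobiliary injury, ICD-10-CM: "K72.10 Chronic hepatic failure without coma K72.11 Chronic hepatic failure with coma", the K73 chronic hepatitis codes, and cirrhosis codes such as "K74.60 Unspecified cirrhosis of liver K74.69 Other cirrhosis of liver".

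Section 9.10 argues that children this young seldom seek care outside the database during baseline, and concludes: "thus prevalent conditions are unlikely to be mistaken for incident events". Later in the same section it accepts that code-only algorithms may overestimate some outcomes.

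**The concern.** The primary objective is the incidence of new events after treatment starts. A code whose descriptor says congenital, chronic, cirrhosis, sequela or late effect does not, on its face, record a new onset within treatment plus 90 days. If a child's cirrhosis predates treatment but is first coded on day 5, the rule counts an incident hepatobiliary injury on IV pantoprazole. The study has no comparator (section 9.1), so nothing cancels such an error, and for an uncommon outcome a few such children could make up much of the count.

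**Working it through.** **1. The plan's own figures.** The protocol gives no figure for this point. Its only computed table, Table 5, uses hypothetical frequencies. All 12 rows reproduce with the Wilson score interval on rounded events divided by N (for example 15/7,489 gives 0.0012 to 0.0033). There is no arithmetic error, and changing the code lists alters nothing in that table.

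**2. Codes sorted by descriptor.**

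| Group | Codes |
|---|---|
| Congenital or past state by wording | D70.0, T78.3XXS, 909.3, 572.8 |
| Chronic or cirrhotic by wording | K72.10, K72.11, K73.x, K74.3 to K74.69, 571.41, 571.49, 571.5, 571.6, 571.8, 571.9 |
| Not shown to be pre-existing | T78.3XXD, K74.00, K74.01, K76.1, 573.0, K71.3 to K71.51 |

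The hepatobiliary row has 20 ICD-9-CM entries and 51 distinct ICD-10-CM entries (K73.9 is printed twice and counted once). The first two groups cover 7 of the 20 (six 571 codes plus 572.8) and 13 of the 51 (2 in K72, 6 in K73 including the K73x entry, 5 in K74).

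**3. What the history exclusion does.** It works on recorded codes. It removes a child whose disease was coded before the index date and keeps one whose disease was present but not yet coded. Guaranteed prior enrollment is 30 days, and the first sensitivity analysis in Table 6 drops even that. History must fall before the index date while follow-up starts on it, so read literally a code first entered on the index date counts as an event. The preterm exclusion and the subgroup definitions, by contrast, include the index date.

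**4. Direction of the bias.** Section 9.10 says late diagnosis lowers the rate because time at risk is inflated. That holds for a new event recorded late. For disease that predates treatment, late recording carries the child past the history exclusion and into the numerator, so the bias is upward.

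**5. Size, as a conversion only.** Let q be the share of children in one outcome's analysis whose only listed code in follow-up is one of the first two groups, and d the mean follow-up in days. Then

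added rate per 1,000 person-years = 1,000 × q × 365.25 / d.

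Neither q nor d is in the documents. With d assumed to be 94 (4 treatment days plus 90) or 60:

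| Assumed q | d = 94 | d = 60 |
|---|---|---|
| 0.05% | 1.9 | 3.0 |
| 0.1% | 3.9 | 6.1 |
| 0.2% | 7.8 | 12.2 |
| 0.5% | 19.4 | 30.4 |

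For scale, take a Cohort 1 outcome with 15 true new events. Person-years are 7,489 × 94 / 365.25 = 1,927, and the rate is 7.8 per 1,000 (exact 95% CI 4.4 to 12.8). With q = 0.1%, 7 events are added and the rate becomes 22/1,927 = 11.4. The 15 is a hypothetical row of Table 5, not an expected count.

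**The case against.** Four points can be made for the plan.

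- **Sensitivity was chosen openly.** Section 9.10 says code-only algorithms were preferred so that safety events are not missed, and that some outcomes may be overestimated. This stands as a general disclosure. It does not mention chronic, congenital or sequela codes, and sensitivity to new events is no reason to count a congenital state as one.
- **The quoted statement on prevalent conditions is about care outside the database.** That is its premise, but its conclusion is worded generally, and the premise does not cover disease not yet coded anywhere.
- **Not every chronic-sounding code is necessarily old.** This stands. A reader might infer that every such entry in the hepatobiliary row (8 of 20 ICD-9-CM, 23 of 51 ICD-10-CM) and both of "T78.3XXD Angioneurotic edema subsequent encounter T78.3XXS Angioneurotic edema sequela" cannot be new. The documents do not support that. A subsequent-encounter code describes the visit, and an event during treatment may first be coded at a later one. Unspecified and early fibrosis state no duration. The toxic-liver codes name a toxic cause, which a drug-safety outcome should keep. The case for K76.1 and 573.0 is weak. Treatment duration has no stated maximum, so the window can exceed 90 days.
- **A child may also carry a retained code.** This stands. Someone with cirrhosis and a follow-up jaundice code (R17) counts either way, so only children whose sole code is in the first two groups add events.

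**Conclusion.** The point holds for the first two groups of codes. For D70.0, T78.3XXS, 909.3 and 572.8 it follows directly from the descriptor. For the chronic hepatitis, chronic hepatic failure, chronic liver disease and cirrhosis codes it is a strong presumption from the wording; the documents do not show that none could arise within the window. That is why those children should be counted separately and not discarded.

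The bias is upward for leukopenia, angioedema, injection site thrombophlebitis and hepatobiliary injury. Its size cannot be estimated from the protocol. A reader might take the conversion above as evidence of material inflation. It is not, because the shares and follow-up lengths are assumptions and the rates ignore censoring and outcome-specific exclusions. The case for a change rests on the definition, and the change is cheap.

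**What to change.** 1. In section 9.4.2, give each affected outcome two lists. The history list keeps every current code. The follow-up event list omits D70.0, T78.3XXS, 909.3, 572.8, K72.10, K72.11, K73.x, K74.3 to K74.69, 571.41, 571.49, 571.5, 571.6, 571.8 and 571.9.
2. Replace parent entries with explicit codes so that omitted codes are not recaptured. K72x would bring back K72.10 and K72.11, and K74, if read as a category, would bring back the cirrhosis codes. Spell out 573 as well for clarity, although with 573.0 kept it covers no omitted code.
3. Keep K71.x, T78.3XXD, unspecified and early fibrosis, K76.1 and 573.0 in the main rate. K74.02 and K74.1 also stay unless the team decides otherwise and records why.
4. Report, per outcome and cohort, the number of children whose only follow-up code is an omitted one, and add a sensitivity rate using the full Table 3 list as it now stands.
5. Reword section 9.10 to say that the history exclusion removes only disease coded before the index date, and that long-standing disease first coded in follow-up would raise the rate.

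The cost is a revised code list, a sentence in 9.4.2, a reworded sentence in 9.10 and one extra run, with no new data. A true new event coded only under an omitted code leaves the main rate, but it stays visible in the separate count and the sensitivity rate. Dropping T78.3XXS leaves a small mismatch with ICD-9-CM 995.1, which has no such split. Dropping D70.0 and 909.3 reduces mismatch, because neither has a congenital or late-effect counterpart listed in the other coding column.

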9. RESEARCH METHODS

9.1. Study design

This will be a retrospective cohort study with no comparator group. No a priori hypotheses are specified. Descriptive analyses including an estimation of incidence rates will be performed.

9.2. **Setting**

The study will be conducted using Optum's longitudinal integrated EHR from the US¹, which is described in Section 9.5 This data source includes data from adjudicated administrative insurance claims, inpatient electronic health records, as well as outpatient EHR enabling capture of exposure to IV pantoprazole in the study population of interest. The study period will be defined from 01 January 2007 to 31 December 2020.

9.3. **Study population**

Two separate cohorts, ie, infants aged 1 month to <1 year and patients aged 1 to <2 years will be identified during the study period using the following inclusion and exclusion criteria.

9.3.1. **Inclusion criteria**

Patients must meet all of the following inclusion criteria to be eligible for inclusion in the study:

- 1. At least one administration of IV pantoprazole during the study period from January 1, 2007 to December 31, 2020, and
- 2. For the cohort of infants aged 1 month to <1 year (Cohort 1): Age 1 month to <1 year on the index date (ie, the date of first administration of IV pantoprazole); For the cohort of patients aged 1 to <2 years (Cohort 2): Age 1 to <2 years on the index date.
- 3. Patients must be enrolled in the database for at least 30 days prior to the index date

In addition to this 30-day lookback window, patients will be further excluded based on the occurrence of a history of outcomes of interest identified in Table 3 occurring prior to the index date.

9.3.2. **Exclusion criteria**

Patients meeting any of the following criteria will not be included in the study:

1. Patients with any of the following ICD-9-CM or ICD-10-CM codes occurring prior to or on the index date indicating a preterm birth or birth weight less than 2.36 kilograms will be excluded:

ICD-9-CM codes: 765.01-765.08; 765.10-765.19; 765.21-765.28

ICD-10-CM codes: P07.21-P07.26; P030-P039; P07.01-P07.03; P07.14-P07.18

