For analyses of estimation of incidence rates of the outcomes of interest during follow-up, each analysis will be restricted to patients without a history of outcome of interest prior to the index date (ie baseline period); thus, for each analysis of a given specified outcome, a distinct sub-cohort will be used (i.e. for the estimation of the incidence of hepatitis, only patients with prevalent cases of hepatitis in the baseline period will be excluded from follow-up and will not contribute to person-time at risk).

For each outcome of interest, patients will be followed from the index date to whichever of the following occurs first (follow-up period):

- Occurrence of an outcome of interest,
- 90 days following the discontinuation of IV pantoprazole administration,
- Initiation of a separate IV pantoprazole infusion within 90 days following the discontinuation of IV pantoprazole administration, where a separate infusion is defined as the subsequent administration at least 7 days from the end of the previous infusion,
- Death,
- End of enrollment in the database,
- End of study period (ie, 31 December 2020).

Incidence rates of each prespecified outcome of interest will be estimated as the number of patients with a specific outcome of interest during the follow-up period divided by the total person-time at risk and reported as incidence per 1,000 person-years with associated 95% CIs, assuming a Poisson distribution. Exact Poisson confidence limits for the estimated rate are found as the Poisson means, for distributions with the observed number of events and probabilities relevant to the chosen confidence level, divided by time at risk.

$$egin{aligned} Y_l &= rac{\chi^2_{2Y,\;lpha/2}}{2} \ Y_u &= rac{\chi^2_{2(Y+1),\;1-lpha/2}}{2} \end{aligned}$$

- where Y is the observed number of events, Yl and Yu are lower and upper confidence limits for Y respectively, $\chi 2\nu$, a is the chi-square quantile for upper tail probability on ν degrees of freedom.

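### In the youngest infants of Cohort 1, the history screen for hepatobiliary injury cannot see newborn-coded jaundice, so persisting jaundice can be counted as a new event

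*Protocol*

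**What the plan says.** The event rule is in section 9.4.2: "The first occurrence of each outcome is defined based on the presence of at least one ICD-9-CM or ICD-10-CM diagnosis code", in the inpatient or outpatient setting during follow-up. The codes are those of Table 3.

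The history rule points to the same table. Section 9.3.1 excludes on a "history of outcomes of interest identified in Table 3 occurring prior to the index date", and section 9.8 adds that "each analysis will be restricted to patients without a history of outcome of interest prior to the index date". No separate list for the history search is given.

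The hepatobiliary row of Table 3 has one jaundice code per coding system: "782.4 Jaundice, unspecified, not of newborn" (ICD-9-CM) and "R17 Unspecified jaundice" (ICD-10-CM). Neither column lists a newborn or perinatal jaundice code.

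Cohort 1 is defined by "Age 1 month to <1 year on the index date", and the minimum lookback is set by "Patients must be enrolled in the database for at least 30 days prior to the index date".

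Among the strengths, section 9.10 concludes: "thus prevalent conditions are unlikely to be mistaken for incident events".

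**The concern.** Leaving newborn jaundice out of the event definition is sensible. The difficulty is that one list serves two purposes. A code whose title excludes newborns is a reasonable event code for an infant older than 1 month. It is a poor history code when the history being searched lies mostly in the newborn period.

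An infant with recorded newborn jaundice therefore enters the risk set as if free of liver history. If the same jaundice continues and a clinician uses a general jaundice code after the index date, a condition that preceded treatment is reported as arising under it. Jaundice also sits in one composite with hepatic failure and hepatitis, so the reported rate would not show how many events came about this way. This affects a safety rate in an age group for which section 7 says no interventional trial data can be obtained from the ongoing study.

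**Working it through.** The protocol states no figure on this point, so there is none to reproduce. The check has two parts: tracing the rules, then an illustrative range.

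**1. Which infants are misclassified**

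| Liver record before index | Liver record after index | Result under the protocol |
|---|---|---|
| Any Table 3 code, including 782.4 or R17 | Any | Removed from the risk set; no error |
| Newborn jaundice code only | None, or newborn codes only | At risk, no event; no error |
| Newborn jaundice code only | First Table 3 liver code, for a new condition | Incident event; correct |
| Newborn jaundice code only | First 782.4 or R17, for the same jaundice | Incident event; error |

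Only the last row is wrong, and it requires a switch of coding after the index date.

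**2. Where it can occur.** An infant indexed at just over 1 month with the minimum 30 days of lookback has a pre-index record that is almost entirely the first month of life. The share falls quickly with age: by 2 months, half of life lies after that first month, leaving time for a general jaundice code before index that would exclude the infant. Cohort 2 is essentially unaffected.

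**3. Whether anything else corrects it.** The exclusion in section 9.3.2 concerns preterm birth and low birth weight, not jaundice in the infants who remain. The first sensitivity analysis in Table 6 drops the 30-day enrollment rule, which does not widen the history search. The second stratifies by coding system with the same lists. Neither addresses this route.

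**4. Coding era.** Section 9.3.3 places the change from ICD-9-CM at October 2015 (stated for subgroups). From 1 January 2007 that is 3,195 of 5,114 study days, or 62%. This is a share of calendar time, not of patients.

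**5. Illustrative size.** From the protocol: 7,489 infants (section 9.6). Assumed: 91 days of follow-up each, and a true frequency of 0.5%.

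- Person-time = 7,489 × 91 / 365.25 = 1,866 person-years.
- True events = 7,489 × 0.005 = 37; rate = 37 / 1,866 × 1,000 = 19.8 per 1,000 person-years (exact Poisson 95% CI 14.0 to 27.3).

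Let m be the share of Cohort 1 in the last row of the table above. False events = 7,489 × m.

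| m (assumed) | False events | Reported rate per 1,000 person-years (95% CI) | Ratio to true |
|---|---|---|---|
| 0.05% | 4 | 22.0 (15.8 to 29.8) | 1.11 |
| 0.1% | 7 | 23.6 (17.1 to 31.7) | 1.19 |
| 0.2% | 15 | 27.9 (20.8 to 36.5) | 1.41 |
| 0.5% | 37 | 39.7 (31.1 to 49.8) | 2.00 |

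With a true frequency of 0.2% (15 events) the ratios run from 1.27 to 3.47; with 1% (75 events), from 1.05 to 1.49.

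**6. A second route to m.** Assume index ages uniform over the 11 months, 5% to 20% with coded newborn jaundice, and 2% to 10% of those first coded 782.4 or R17 in follow-up.

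- Ages 1 to <2 months: 7,489 / 11 = 681 infants; 681 × 0.05 × 0.02 = 0.7 and 681 × 0.20 × 0.10 = 13.6 false events.
- Ages 1 to <3 months: 7,489 × 2 / 11 = 1,362 infants; 1.4 to 27.2 false events.

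The low ends are negligible and the high ends are not. None of the percentages comes from the protocol.

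**The case against.** The title of code 782.4 also protects the numerator: jaundice that continues under newborn codes is never counted. A first general jaundice code after 1 month of age may be a genuine new liver signal. Both points stand, and they limit the error to the last row of the first table above.

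A reader might infer that section 9.10 contradicts the design. It does not quite do so. Its stated reason is that care is rarely sought outside the database, which concerns data capture rather than the match between code lists. The same section concedes outcome misclassification and that sensitive algorithms may overestimate some outcomes. What remains is that its conclusion about prevalent conditions is wider than its reason: a condition recorded inside the database under an unlisted code is not covered.

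R17 carries no newborn exclusion in the protocol, so the ICD-10-CM side rests only on the absence of a newborn code from Table 3. This weakens that half without removing it.

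The study is descriptive, with no comparator, and this touches one component of one of 25 outcomes. Section 9.8 also allows the analysis plan to modify the methods. That bears on priority; the protocol's own rule still ties history to Table 3.

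**Conclusion.** The gap is real and follows from the protocol's own rules: in infants indexed shortly after 1 month of age, newborn-coded jaundice does not count as history, and a first 782.4 or R17 code afterwards counts as incident hepatobiliary injury. The direction is upward.

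The size cannot be derived from the protocol. It may be negligible or may add a material number of events, depending on how often newborn jaundice is coded before index and then recoded. The effect is confined to the youngest part of Cohort 1.

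Three stronger readings are not supported. First, Table 5 gives no expected number of hepatobiliary events against which to set the false ones; its frequencies are hypothetical and tied to no outcome. Second, the documents do not show the same problem for other outcomes, because no newborn-specific code for them is cited anywhere. Third, the event codes themselves are not shown to be wrong.

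**What to change.** Leave the event codes unchanged. For hepatobiliary injury in Cohort 1 only, treat a newborn or perinatal jaundice or liver code recorded in the 30 days before, or on, the index date as prevalent disease. Alternatively, and at the least, add a sensitivity analysis that either excludes infants with such codes or drops 782.4 and R17 from the event. In section 9.10, limit the statement on prevalent conditions to events missed because care was sought elsewhere, and name this route as a remaining source of error.

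The time window matters. History now means any earlier record, so an unrestricted newborn list would also remove older infants whose jaundice resolved long ago. On the assumed 5% to 20%, that is 7,489 × 0.05 = 374 to 7,489 × 0.20 = 1,498 infants. With the 30-day window, if newborn codes fall in the first month of life, those affected are essentially infants indexed at 1 to <2 months: at most 681 × 0.05 = 34 to 681 × 0.20 = 136.

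The cost is one short code list, applied to data already loaded, and a small loss of person-time for this outcome among the youngest infants. Some infants whose jaundice had already resolved would be removed, and a newborn code older than 30 days would still be missed. The version without 782.4 and R17 avoids both limits but also loses true jaundice events.
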